Descriptive statistics (means, SD, and frequencies) will be calculated and Q-Q plots of residuals used to test for normality and skewness. Significance will be set at $P<0.05$. Data with a time component will be analyzed using a linear mixed effects model with subjects as a random factor and condition and time as fixed factors using SAS. Main effects of condition and condition X time interactions will be probed with planned comparisons to examine differences between β -OHB and placebo at each time point. Data with skewed distributions will be log-transformed or non-linear mixed effects models will be used. All participants will be included in the intention-to-treat (ITT) analyses and missing data will not be imputed, per contemporary guidelines with use of linear mixed models [16].

Sample Size

Twenty participants will be included in this cross-over study. In our pilot study on healthy volunteers we saw a ~15% reduction in glucose area under the curve after

ketone supplementation versus placebo. Using means and standard deviations from our previously published study in people with T2D (N=51) [17] for fasting glucose (8.6 +/- 2.3) a 15% reduction in blood glucose corresponds to an effect size $d = 0.73$. Assuming 80% power with an alpha level of 0.05 and a moderate correlation between repeated measures of $r=0.7$ (calculated using G*Power v3.1) a total sample size of $n=14$ is needed to detect differences between ketone and placebo conditions. To preserve power and account for any dropouts or missing blood samples we will recruit 20 participants, aiming for equal males and females.[2][17]

Significance

The results of this study will help determine whether supplementation with exogenous ketones can alter metabolism and subsequently improve blood glucose levels. This is a pilot study and it will provide useful data to better answer future research questions and aid in the design of longer term studies.

OUTCOMES MEASUREMENTS AND METHODS

The primary outcome measure is the plasma glucose concentrations over the 3-hour period following the ingestion of the beverages. Secondary measures will include plasma insulin and C-peptide, free fatty acids, inflammatory cytokines, CBF, cognitive function and neurovascular coupling, inflammation signalling molecules, appetite/satiety levels and gastrointestinal distress questionnaire.

Anthropometric Measures

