Waist circumference, height (cm) and weight (kg) will be measured using standard procedures. Body mass index (BMI) will be calculated as kg/m^2 .

Physiological Measures

Resting blood pressure and heart rate will be collected for descriptive purpose. Before both measures, participants will be instructed to sit quietly and rest for 5 minutes. A finger tip heart rate monitor will track heart rate. Blood pressure will be collected using a cuff around the upper arm, a stethoscope will be placed in the cubital fossa for systolic and diastolic blood pressure.

Blood Sampling

Venous blood samples for plasma glucose, insulin, free fatty acids, C-peptide and cytokines will be obtained by a researcher trained in phlebotomy ([name] and Dr.

[name]). Repeated blood samples will be obtained by intravenous catheter in an antecubital vein kept patent with sterile saline. The procedure will follow sterile conditions within our laboratory ([name]) with biosafety and blood collection accreditation as approved previously (e.g., H14-01636; H15-00205; H12-02268). Approximately 5 mL of blood will be collected into vacutainer tubes and processed at 7 timepoints for a total of 35 mL per test day. Plasma insulin will be measured on a 96-well plate using a commercially available high-sensitivity human insulin ELISA (Mercodia, Upsalla, Sweden). Plasma glucose will be measured using a hexokinase method and free fatty acids by colorimetric assay. Glucose, insulin, free fatty acids and cytokines will all be analyzed on a Chemwell 2910 clinical chemistry analyzer (Awareness Technologies, Connecticut, United States of America). C-peptide will be measured by ELISA (Millipore #EZHCP-20K). Plasma will also be analyzed through metabolomics technology by UVic-Genome BC Proteomics Centre. De-identified samples containing frozen plasma in microtubes (samples identified by an ID code only with no personal identifiers) will be sent on dry ice to UVic following UBC Biosafety guidance for transmission of biological materials. Results containing the analyte concentration are sent by secure email back to UBC PI.

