2. Paired t-test on peak blood glucose concentration (i.e., highest blood glucose value measured after ingestion of supplement or placebo)
3. Paired t-test on peak blood glucose concentration above baseline (i.e., highest blood glucose value above fasting baseline after ingestion of supplement or placebo)
4. Paired t-test on blood glucose total area under the curve (i.e., glucose above zero across 180 minutes after ingestion of supplement or placebo)

Secondary outcome measures:

Secondary outcomes will be analyzed similarly to the primary outcome using a linear mixed effects model. Secondary and exploratory blood marker outcomes that are below or above the detection limit, will be imputed as limit of detection (LOD) / $\sqrt{2}$ or $LOD * \sqrt{2}$, respectively [4]. Preregistered secondary outcomes include:

1. Metabolic outcomes (plasma insulin, plasma c-peptide, plasma free fatty acids, plasma β -OHB)
2. Markers of brain/cognitive function (intracranial blood flow measured by ultrasound, blood pressure measured manually, cognitive function using BrainBaseline on an iPad, brain-derived neurotrophic factor)
3. Markers of inflammation (plasma tumour necrosis factor alpha, plasma interleukin-1 β , plasma interleukin-6, total blood monocytes and monocyte subsets, monocyte histone acetylation)
4. Markers of appetite (self-reported hunger and fullness assessed via a 0 to 100 mm Visual Analog Scale, gastrointestinal symptoms assessed via a 0 to 100 mm Visual Analog Scale, total energy consumed in kilocalories during a buffet style meal at the end of testing)

Exploratory outcomes measures:

Exploratory outcomes will be analyzed similarly to the primary outcome using a linear mixed effects model.

Exploratory outcomes that were not preregistered include:

1. Metabolomics
2. Electrolyte status, lactate, pH etc.

REPORTING RESULTS

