We will summarize data (including participant baseline characteristics) as mean \pm standard deviation (SD) for continuous and N (%) for categorical data. A significant effect will be concluded at two-sided P -value of < 0.05 . We will report on the effect of condition and the interaction of the treatment effect over time. Effect estimates from the model alongside 95% confidence intervals around the mean differences in the outcome after accounting for the included covariates will be reported. Changes in outcome within condition (e.g., effect of ketone monoester on blood glucose at 180 minutes compared to baseline) will be reported via mean differences with SD outside the model, if applicable. Effect sizes (Hedges' g) will be stated.

PROGRAMMING PLAN

Statistical analysis will be performed after the last patient out, using R [5].

REFERENCES

1. Myette-Côté, É., et al., Prior ingestion of exogenous ketone monoester attenuates the glycaemic response to an oral glucose tolerance test in healthy young individuals. *The Journal of Physiology*, 2018. **596**(8): p. 1385-1395.
2. Francois, M.E., et al., Combined interval training and post-exercise nutrition in type 2 diabetes: a randomized control trial. *Frontiers in Physiology*, 2017. **8**: p. 528.
3. Chakraborty H. A mixed model approach for intent-to-treat analysis in longitudinal clinical trials with missing values [Internet]. 2009. Available at: <http://www.rti.org/publication/mixed-model->

approach-intent-treat-analysis-longitudinal-clinical-trials-missing-values

4. Canales R.A., et al. Methods for handling left-censored data in quantitative microbial risk assessment. *Appl Environ Microbiol* 2018. **84**(20): e01203-18.
5. Team RC. A Language and Environment for Statistical Computing. R Foundation for Statistical Computing 2020. Available at (accessed November 4, 2021): <https://www.r-project.org/>
- 6.

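### The SAP's P<0.05 rule is not confined to the primary outcome: it reaches 18 to 26 secondary measures and an unsized metabolomics panel with no multiplicity control or nominal label

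*SAP*

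**What the plan says.** The decision rule is in the SAP under Reporting Results: "A significant effect will be concluded at two-sided" P<0.05. It follows the listing of all outcome classes and names none of them. The next sentence sets what each model delivers: "We will report on the effect of condition and the interaction of the treatment effect over time".

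The outcome sections carry the primary's model across. For the secondary outcomes: "Secondary outcomes will be analyzed similarly to the primary outcome using a linear mixed effects model". For the exploratory ones: "Exploratory outcomes will be analyzed similarly to the primary outcome using a linear mixed effects model". The exploratory list contains metabolomics and an open-ended set of electrolyte, lactate and pH measures. The Protocol confirms the metabolomics under Blood Sampling ("Plasma will also be analyzed through metabolomics technology by UVic-Genome BC Proteomics Centre") but gives no number of analytes.

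The Protocol's Statistical Analyses section uses the same threshold ("Significance will be set at" P<0.05) and adds tests at individual time points: "Main effects of condition and condition X time interactions will be probed with planned comparisons to examine differences between" the two drinks at each time. The SAP does not repeat these.

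Neither document gives an adjustment, a testing order, false discovery rate control, or a statement that secondary results are descriptive. They do name a single preregistered primary outcome, list the secondary outcomes separately, label metabolomics and electrolytes as exploratory and not preregistered, and call the study a pilot. The SAP also commits to effect estimates, 95% confidence intervals and Hedges' g.

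**The concern.** The rule speaks of concluding an effect. Applied as written, any secondary or exploratory result below 0.05 becomes a claimed effect of the ketone drink, however many were examined. The Protocol states directional hypotheses for fatty acids, inflammation, neurovascular coupling, cognition, BDNF, histone acetylation and satiety, so such claims are foreseeable. It also says that the pilot will help plan longer studies. A chance finding in about 20 people, reported as significant, could therefore shape what is studied next. The exposure is largest for metabolomics, where the number of tests is not fixed anywhere.

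**Working it through.** The documents give no error-rate figure for these outcomes, so there is none to reproduce. The check counts the tests and applies the 0.05 rule.

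**Number of secondary measures** (SAP secondary list, with Protocol detail)

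| Group | As named | Composites split |
|---|---|---|
| Metabolic | 4 | 4 |
| Brain and cognition | 4 | 8 (2 arteries, systolic and diastolic pressure, 3 cognitive tests, BDNF) |
| Inflammation | 6 | 8 (assuming 3 monocyte subsets; the number is not stated) |
| Appetite | 4 | 4, or 6 if all four appetite scales are analysed |
| Total | 18 | 24 to 26 |

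**Number of tests**

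- Start from 24 and drop β-OHB, which the drink is designed to raise: 23 condition tests.
- Add the condition-by-time test where repeated times are plausible. Buffet energy intake has one value per condition, and the only stated GI assessment is at 30 minutes, so both lose the interaction: 23 × 2 − 2 = 44 tests. This is a high count, because sampling times for some measures are not given.
- The Protocol's comparisons at each time point are not counted.

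**Expected false positives if all nulls are true** (k × 0.05; correlation does not change this)

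- 23 × 0.05 = 1.15
- 44 × 0.05 = 2.2
- If only half of the 44 nulls are true: 22 × 0.05 = 1.1

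**Chance of at least one, independent tests** (1 − 0.95^k)

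- k = 23: 69%
- k = 44: 89.5%

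**Chance of at least one, correlated outcomes.** Simulated with 100,000 draws of equally correlated normal test statistics at two-sided 0.05, all nulls true. Where two effects are counted, condition and interaction are taken as independent of each other.

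| Tests | ρ = 0 | ρ = 0.3 | ρ = 0.5 | ρ = 0.7 |
|---|---|---|---|---|
| 24 condition tests only | 71% | 60% | 46% | 31% |
| 22 outcomes × 2 effects | 90% | 82% | 69% | 51% |
| 24 outcomes × 2 effects | 91% | 84% | 70% | 52% |

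If the condition and interaction statistics share the same correlation as well, 46 tests give 78%, 60% and 40% at ρ = 0.3, 0.5 and 0.7.

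**Metabolomics.** The panel size is assumed, because the documents do not give it. On the condition effect alone, with all nulls true:

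- 50 metabolites: 50 × 0.05 = 2.5 expected false positives
- 150 metabolites: 150 × 0.05 = 7.5
- 500 metabolites: 500 × 0.05 = 25

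Testing the interaction as well doubles these.

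**The primary itself.** The model yields two effects, and the SAP does not say which one decides. If either counted and they were independent, the error rate would be 1 − 0.95² = 9.75%. Four further paired t-tests on glucose, which the SAP calls confirmatory, use the same threshold. Five independent tests would give 1 − 0.95⁵ = 22.6%; these are analyses of the same glucose curves, so the real figure would be lower.

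**The case against.** The strongest reply is that the structure already guides the reader. One outcome is preregistered as primary, metabolomics is labelled exploratory, and the study is a 20-person pilot. Many statisticians would not require formal adjustment of secondary outcomes in such a study. This stands in part. Secondary and exploratory tests do not inflate the primary's type I error, and whether to apply Holm or Benjamini-Hochberg to the secondary outcomes is a trade-off on which the point does not depend. What the labels do not do is change the decision rule, which reaches all outcome classes.

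A second reply is that the counts are worst cases. That also stands. Insulin with C-peptide, total monocytes with their subsets, and hunger with fullness are likely to be correlated. Several effects are hypothesised to be real, and each true effect removes a possible false positive.

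Three stronger readings are tempting and should be resisted:

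- A reader might infer that false positive claims are close to certain. The listed secondary outcomes do not support that. Near-certainty needs a large metabolomics panel with weakly correlated analytes, and the documents state neither.
- A reader might infer two tests for each secondary measure. This fails for energy intake and is doubtful for GI symptoms.
- A reader might infer that the sponsor decided against adjustment. The documents are silent on adjustment; they state only the threshold.

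**Conclusion.** The point holds in a limited form. The SAP has one significance rule, not confined to the primary outcome, and nothing that adjusts or qualifies the secondary and exploratory results. For the listed secondary measures, about 1.2 false positives are expected from 23 condition tests and about 2.2 from 44 tests. With both effects counted, the chance of at least one is at most about 90%, and roughly 50-84% at correlations of 0.7 to 0.3. These figures assume three monocyte subsets and that every null is true, so they are upper bounds. The correlated range also assumes that the condition and interaction tests are independent of each other; it is lower if they are not.

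For metabolomics the firm statement is 0.05 false positives per null metabolite and effect tested; any total depends on an assumed panel size. The result of the primary analysis is not put at risk by these families. The undeclared choice between its two effects is a separate gap that the same edit should close.

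**What to change.** Amend Reporting Results in the SAP:

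- Limit the significance conclusion to one named primary glucose test. State whether the condition effect or the condition-by-time interaction decides it, and call the four additional glucose t-tests supportive.
- For metabolomics, test the overall condition effect once per metabolite, apply Benjamini-Hochberg control at a 5% false discovery rate across all measured metabolites, and report how many were tested.
- For the secondary and remaining exploratory outcomes, report the estimates and 95% confidence intervals already planned, with P-values labelled nominal and no claim of significance.

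The cost is a few sentences and a few lines of R, with no new data or design change. If the analysis has already been run, the same labels and the metabolite correction can be applied in the report. The downside is that fewer secondary and metabolite results can be called significant. This is a cheap improvement; it does not correct an error in the primary analysis.
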